**CONFIDENTIAL**

056-F275 Rev G Clinical Investigation Plan Template

## 10.10.2 Study Completed

At the completion of the 2-year follow-up visit subjects will be exited from the study. The 2-year Follow-Up visit and Exit visit should be combined, and both the 2-year Follow-up eCRF and the Study Exit eCRF need to be completed.

## 10.10.3 Lost to Follow-up

Every attempt will be made to contact subjects whose status is unknown, including at a minimum:

- Three phone calls with each attempt clearly documented in the source documents including response or lack thereof.
- If there is no response to the phone calls, then a certified/registered letter should be written to the subject. A copy of the letter should be retained in the subject's source document.

To ensure all efforts have been made, the site should check public health records to identify vital status.

A subject will not be considered lost to follow-up prior to the 1-year visit window closure. A subject would not be considered lost to follow-up until all efforts to obtain current status have been exhausted per the attempts noted above (including review of medical charts and public health records).

In addition, regulation set forth by the governing IRB must be followed.

## 10.10.4 Subject Chooses to Exit (i.e., Revokes Consent)

A subject can withdraw from the study at any time. If the subject wishes to exit from the study (i.e., the subject revokes consent), the study site is required to document the reason for exit on the Study Exit CRF. In addition, study sites shall follow the regulations set forth by the governing IRB. If possible, the following data should be collected prior to subject withdrawal:

- Reason for exit

## 10.10.5 Investigator Withdraws Subject

No subjects should be withdrawn by Investigators unless compelling medical justification is present. It is recommended Investigators discuss any withdrawals with the study team prior to withdrawing subjects. If an Investigator Withdrawal is necessary, the following data should be collected prior to subject withdrawal if possible:

- Reason for subject withdrawal

## 10.10.6 Conditional Disengagement

After a subject is enrolled every effort should be made to keep the subject in the study. However, it is recognized that there are circumstances where limited data may be collected, or study exit will need to occur. In these cases, we will consider either modified data collection requirements where subjects may conditionally disengage in study procedures but data from the subject can still be collected because the subject has not revoked consent or exit when study participation is completely ended.

Subjects may be conditionally disengaged from study procedures for any of the following reasons:

*Medtronic Business Restricted*

- Subject chooses to disengage (e.g., follow-up schedule cannot be adhered to, study burden too large, relocation to another geographic location but telephone follow-up still acceptable)
- Investigator deems conditional disengagement necessary (e.g., medically justified)

If the subject wishes to disengage from the study, or the Investigator deems it necessary, the study site is required to document the reason. Data collection requirements no longer apply, but study sites are encouraged to collect as much data as possible on the eCRFs.

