## 9.2 Subject Enrollment

A subject is considered enrolled in the study when the informed consent form is signed and dated. As soon as the surgical procedure has begun with the Medtronic Hugo™ RAS system, the subject must be followed regardless of whether the subject completed the surgical procedure with the Medtronic Hugo™ RAS system. Subject enrollment will be consecutive at the institution according to required procedure types and eligibility criteria. See **Section 14** for additional details.

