## 12 Adverse Events and Device Deficiencies

### 12.1 Adverse Events

All AEs, including non-subject AEs, will be collected throughout a subject's participation, starting from the time the informed consent form is signed, through 30 days after the day of the procedure, regardless of their severity, relationship to the Hugo™ RAS system or study procedures.

After 30 days, all AEs will be assessed by the surgeon and those AEs deemed attributable to the procedure and / or study device will be reported. All deaths will be collected throughout a subject's participation, regardless of relatedness.

Reporting of these events to Medtronic will occur on an AE Form, including event description, date of AE, treatment, resolution, assessment of both the seriousness of the AE and the relatedness to the study device, procedure. Each AE must be recorded on a separate AE eCRF.

AE definitions used in this study (**Table 8**) are based on ISO 14155:2020 (Clinical Investigation of Medical Devices for Human Subjects – Good Clinical Practice). Documented pre-existing conditions are not considered AEs unless the nature or severity of the condition has worsened. See **Section 14** for details regarding AE analyses in each study analysis set. In addition, AEs impacting users or other persons (non-subject AEs) will be collected on a non-subject AE CRF.

Any unresolved procedural or device-related events that are still ongoing past study exit will be monitored by the Investigator per their institutional standard-of-care.

Unavoidable adverse events (UAE) (those that are inherent to the procedure and are expected to occur in all subjects for an expected duration) listed in **Table 11** will not be captured or reported unless the adverse event worsens or persists outside the stated timeframe post procedure. **Section 11.1** includes a list of several but not all-encompassing anticipated adverse events.

All Serious Adverse Events (SAE), deaths, and Surgical Site Events (SSEs) will be adjudicated by an independent CEC through 30 days post-procedure as of revision 5.0 of the protocol.

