### **14.11 Missing Data Handling**

The primary effectiveness analysis will be based on the FAS. If 5% of the data or fewer are missing for the analysis, no imputation will be used. Otherwise, missing data will be imputed for the FAS using multiple imputation (MI). The model variables used for the MI analysis may include baseline variables such as age, gender, and BMI. Ten imputations will be conducted and combined using the Rubin's rule. Sensitivity analysis will be performed using available data in both FAS and PPAS as well as tipping-point analysis in FAS to fully understand the missing data impact on the study results.

The primary safety analysis will be based on the FAS subjects with available data at 30-days, i.e. whose status (event, no event) at 30-days can be determined. No imputation will be conducted.

For the secondary and ancillary endpoints, analysis will be conducted with available data in FAS. No imputation will be conducted.

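### Conditional disengagement makes 30-day safety data optional for subjects still under consent, against the AE-collection rule and with no required minimum for SSE status

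*Protocol*

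**What the plan says.** Protocol 10.10.6 describes a status between full participation and exit. It is open to subjects who choose it and to subjects for whom the investigator judges it necessary. The section pulls in two directions:

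- It begins with modification: "we will consider either modified data collection requirements where subjects may conditionally disengage in study procedures". It adds that "data from the subject can still be collected because the subject has not revoked consent", and one of its example reasons is "relocation to another geographic location but telephone follow-up still acceptable".
- It ends with release: "Data collection requirements no longer apply, but study sites are encouraged to collect as much data as possible on the eCRFs". The site must document the reason, and nothing else is kept as a requirement.

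Other sections set duties with no exception for disengaged subjects:

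- Protocol 12.1: "All AEs, including non-subject AEs, will be collected throughout a subject's participation". The sentence goes on to run from consent through 30 days after the procedure, whatever the severity or relatedness. After day 30, AEs attributable to the procedure or device are reported, and deaths are collected throughout. Section 12.4 repeats this.
- Protocol 9.2: once the procedure has begun, "the subject must be followed regardless of whether the subject completed the surgical procedure with the Medtronic Hugo™ RAS system".
- Protocol 10.10.3: before a subject counts as lost to follow-up, the site must make three documented calls, send a certified letter, and review medical charts and public health records.

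On analysis, Protocol 14.11 says "The primary safety analysis will be based on the FAS subjects with available data at 30-days", with no imputation. SAP 7.4 defines which subjects have available 30-day data.

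**The concern.** A consenting, reachable subject gets weaker mandatory ascertainment than one who has disappeared. For the second, the site must call, write and check the chart. For the first, it is only encouraged to collect what it can.

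This reaches the primary safety endpoint. The analysis set depends on whether 30-day SSE status is known, and 10.10.6 leaves it to each site whether that status is recorded for disengaged subjects. Multiple imputation and the tipping-point analysis are planned for effectiveness only, so no planned analysis would show the effect of missing safety status. The CEC cannot adjudicate an event that was never reported. The same gap affects related AEs, readmission, reoperation and recurrence through 2 years.

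**Working it through.** **1. The plan's own figure.** Inputs from SAP section 6: performance goal 30%, expected rate 15%, one-sided alpha 0.0125, n = 86 per cohort, 10% attrition. Test: exact binomial (Protocol 14.4.2).

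- Pass limit: the largest c with P(X ≤ c | n, 0.30) ≤ 0.0125. For n = 86, c = 16, because P(X ≤ 16 | 86, 0.30) = 0.0118 and P(X ≤ 17 | 86, 0.30) = 0.0223.
- Power: P(X ≤ 16 | 86, 0.15) = 0.861. The stated 86% is reproduced.
- Enrolment: 86 / 0.90 = 95.6, so 96. This is also reproduced.
- With status known for all 96, c = 18 and power is 0.878. Missing status within the attrition allowance therefore costs little power. The exposure is bias.

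**2. What happens to a disengaged subject who misses the 30-day visit (SAP 7.4).**

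| Situation | Treatment in the analysis |
|---|---|
| No follow-up visits, SSE reported | Counted as an event |
| No SSE recorded, another visit in or after the 30-day window, up to the 3-month visit | Counted as no event |
| No SSE recorded, no qualifying visit | Status unknown, dropped |

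An SSE that occurred but was not reported falls in the second or third row.

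**3. Illustration.** The documents give no disengagement rate. Assume 96 treated subjects in a cohort, 20 with an SSE, and 10 lapsed subjects (96 − 86, the whole all-cause attrition allowance). p is P(X ≤ x | n, 0.30). Holm's thresholds are 0.0125 for the smaller p-value and 0.025 for the larger, the latter only if the smaller is significant.

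| Case | Analysed | p | At 0.0125 | At 0.025 |
|---|---|---|---|---|
| All status known | 20/96 | 0.029 | fail | fail |
| 4 SSEs among the 10 dropped | 16/86 | 0.0118 | pass | pass |
| 3 SSEs among the 10 dropped | 17/86 | 0.022 | fail | pass |
| 2 SSEs among the 10 dropped | 18/86 | 0.040 | fail | fail |
| 2 SSEs reported, 8 event-free subjects dropped | 20/88 | 0.082 | fail | fail |

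The third case in the table passes only if the other cohort has already passed at 0.0125. The first reversal needs a 40% SSE rate among the lapsed (4/10) against 18.6% in the rest (16/86).

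**4. Error rate under assumed differential loss.** Let the true rate be 30%, with 10 of 96 dropped at SSE rate q. The rate among those analysed is (0.30 × 96 − 10q) / 86, and the pass limit stays at 16/86.

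- q = 30%: rate 30.0%, false-pass probability 1.2%
- q = 45%: rate 28.3%, false-pass probability 2.7%
- q = 60%: rate 26.5%, false-pass probability 5.8%

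The values of q are assumptions. Nothing in the documents supports a particular one.

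**The case against.** The strongest reply has four parts.

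- **The requirement lapses, not the collection.** Sites are encouraged to collect, telephone contact is named in one example, and every effort is to be made to keep the subject in the study. This stands. A reader might infer that all data collection stops, and the section does not say that.
- **Other duties are not expressly cancelled.** AEs must be followed until resolution or study exit (footnote 2 to Table 7, and 12.3), and a disengaged subject has not exited. SAE, UADE and death reporting (Table 10, 12.6) carries no exception. This is a fair reading, but it is exactly the conflict. One section says that collection requirements no longer apply, others keep AE requirements in force, and the protocol does not say which governs.
- **Section 9.2 concerns something else.** Its sentence is about subjects whose robotic procedure was not completed, and 10.10 openly allows exit and withdrawal. This stands. A flat contradiction with 9.2 might be inferred, but the firm conflict is with 12.1 and 12.4.
- **Favourable bias is not shown.** SAP 7.4 counts a reported event even with no visits, while an event-free subject with no qualifying visit drops out. Where sites report events, this pushes the observed rate up, as 20/88 shows. The reversal to 16/86 uses the whole attrition allowance and a lapsed-subject SSE rate about twice that of the rest. This stands as a limit on size. It does not remove the gap, because counting an event depends on a report that 10.10.6 makes optional.

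A reader might also want investigator-initiated disengagement held to the standard in 10.10.5 ("No subjects should be withdrawn by Investigators unless compelling medical justification is present"). The documents do not require that. Disengagement is the milder alternative to exit, and 10.10.6 gives medical justification as its example ground.

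**Conclusion.** The concern holds in a limited form. Section 10.10.6 makes everything except the reason for disengagement optional for subjects still under consent, and sets no minimum for 30-day SSE status. This conflicts with 12.1 and 12.4, sits awkwardly with 9.2, and falls below the mandatory effort for lost-to-follow-up subjects. The change should be made. It is a stated rule that can lose or misclassify primary-endpoint data, and it is cheap to correct.

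The size is illustrative only. Under the assumptions in the working, four unreported SSEs among ten lapsed subjects reverse a cohort's result at 0.0125, three do so only at Holm's second step, and two do not. It would go too far to infer that SSE status is automatically lost or that the safety result will be biased towards success. The planned power and sample size are unaffected.

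**What to change.** Reconcile 10.10.6 with 12.1 and 12.4 by replacing the release sentence with text to this effect:

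*Scheduled in-person visits and questionnaires may be waived. Unless the subject revokes consent, the following remain required, by telephone or medical-record review at the existing time points: all AEs, including SSE status, through day 30; and afterwards deaths, procedure- or device-related AEs, readmission, reoperation and suspected recurrence. A recurrence not confirmed by investigator examination is reported as subject-reported, as in 5.2.2.*

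Keeping all AEs through day 30, and not SSEs and SAEs alone, is needed to remove the conflict with 12.1 and to protect the Clavien-Dindo Grade I or higher secondary endpoint. The recurrence sentence is needed because a telephone report cannot establish clinical recurrence under 5.2.2.

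The cost is a short protocol amendment and a call or chart check for a few subjects by existing site staff. The protocol already uses both methods: telephone contact in 10.1.4 to 10.1.6, and calls and chart review in 10.10.3.

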## **11 Risks and Benefits**

### **11.1 Potential Risks**

Medtronic follows rigorous Quality Assurance and Control procedures throughout the life of a product, from the business analysis phase through development, market release, and post-market surveillance. The Medtronic risk management process follows ISO 14971:2012, Medical Devices – Application of Risk Management to Medical Devices and applicable requirements of YY/T 0316-2008 Medical devices—Application of risk management to medical devices (ISO 14971: 2007, IDT).

The Risk Management Report (RE00308824) summarizes the risk management activities for the Hugo™ RAS system as stated in the Risk Management Plan (R0057077), as well as the overall acceptability of risk. The Risk Management Report addresses risks resulting from the interaction between the user, the subject, and the device. It does not focus on risks inherent to medical treatment enabled by the Hugo™ RAS system. This risk analysis assumes that the product shall only be operated by qualified, properly trained medical personnel. While every attempt has been made to reduce subject and user risks, all surgeries using the Hugo™ RAS system carry some residual risk, even when used by trained physicians.

Specific details of hazardous situations, causes, and risk control measures are identified in the Risk Analysis Chart (RE00027518). Hazardous situations as described in the Risk Management Plan, their associated harms, and specific device benefits to mitigate these hazardous situations are identified below.

- Arrhythmia
- Bleeding
- Blunt Trauma
- Bowel Perforation
- Burn (varying degrees)
- Burn, Bowel
- Burn, Thermal
- Crushing Injury
- Damage to equipment/facility

*Medtronic Business Restricted*

- Delay of Treatment (prolonged procedure)
- Electrical Shock
- Foreign Body in Subject
- Implant, Failure of
- Infection
- Inflammation
- Tissue Damage/Tissue Trauma
- Toxicity
- Vessel Perforation

The incidence of these risks may be different than anticipated due to unknown circumstances or medical conditions.

There may be other discomforts and risks related to the Hugo™ RAS system and/or this study that are not foreseen at this time. In addition, the Hugo™ RAS system for inguinal and ventral hernia repair indications is investigational in the United States and may be no more or less safe or effective than other commercially available robotic surgery systems.

The study sponsor may decide to stop the study before obtaining approval of the investigational product but will continue to guarantee subjects safety.

## 11.2 Risk Minimization

The potential risks associated with the Medtronic Hugo™ RAS system were identified and have been successfully mitigated. Medtronic has further minimized the possibility of risks by performing required laboratory and preclinical testing prior to this clinical study and implementing quality control measures into production processes.

Any potential risks associated with participation in this study are further minimized by providing guidelines for subject selection and evaluation, providing adequate instructions and labeling, selecting qualified investigators, and training study personnel on the safe use of the device and on the CIP procedures.

Medtronic has also attempted to minimize risk to subjects by using an external, independent CEC to review safety issues identified as part of the study.

The potential risks associated with the Medtronic Hugo™ RAS system have been identified above and will be constantly monitored, assessed, and documented by the Investigators and sponsor.

## 11.3 Potential Benefits

The Hugo™ RAS system may offer no benefit. As with commercially available robotic surgery systems, the potential benefits of undergoing inguinal and ventral hernia repair surgery using the Hugo™ RAS system may include lower complication rates compared to traditional laparoscopic and open surgical procedures

*Medtronic Business Restricted*

**(Section 6.2.1).**

As described in **Section 6.2.1**, the safety and performance of commercially available RAS systems have been evaluated in the literature search showing that robotic assisted surgery was comparable or superior to open or traditional laparoscopic surgery in most comparisons.

Other benefits listed below may more directly impact surgeon performance, although ultimately, they affect the end result of subject outcomes and thus are important safety and performance factors.

- Better ergonomics and less strain or fatigue for the user. The torque forces are delegated to the robotic arms, which decreases the strain on surgeon's muscles in the neck, shoulders, and back.
- Mitigation of hand tremors, which results in fewer surgeon errors.
- Better 3D visualization of surgical field for the console surgeon. The camera is controlled by the surgeon and not the assistant. The trainees see what the surgeon is seeing at the console, albeit in 2D rather than 3D.
- Lack of fulcrum effect. This factor helps to shorten the learning curve for RAS use.
- Shorter learning curve compared to traditional laparoscopic surgery.

The data collected from this study will also help characterize the safety and performance of the Hugo™ RAS system. If the results of this study support additional clinical research, further studies may be justified to evaluate the potential for improved standard-of-care using robotic assisted inguinal and ventral hernia repair surgery.

This study does not exclude any adults based on age; therefore, this risk-benefit rationale should be generalizable to Medicare beneficiaries who qualify for a robotic assisted inguinal and ventral hernia repair surgery.

## **11.4 Risk-Benefit Rationale**

As described in the Risk Management Report (RE00308824), use of the Hugo™ RAS system involves residual risk. The established controls provide adequate assurance that the identified potential risks described above have been eliminated, reduced to an acceptable level, or deemed acceptable. These controls will ensure that a consistently safe and effective product is produced for the intended user.

In addition, cadaver studies, human factors/usability testing and product validation labs demonstrate that the Hugo™ RAS Platform performs as intended. Verification testing shows that the Hugo™ RAS Platform meets all product and system design input requirements. The clinical literature (**Section 6.2.1**) provides relevant patient experience for RAS. The safety and performance of commercially available RAS systems are supported by the observation that length of hospital stay, complication rate, level of intra-operative blood loss, complications, and conversion rates were comparable or superior to conventional laparoscopic or open technologies (**Section 6.2.1**).

In conclusion, the contributions of the Hugo™ RAS system to subject outcomes substantially outweigh the minimal reported risks and side effects associated with the use of this device. The overall residual risks associated with the Hugo™ RAS system have been determined to be acceptable. Therefore, these assessments present a favorable benefit/risk profile and justify the use of the product in humans and an

*Medtronic Business Restricted*

evaluation of clinical data relevant to the proposed investigation.

## 11.5 Risk Determination

The Hugo™ RAS system and instruments are considered significant risk.

## 12 Adverse Events and Device Deficiencies

### 12.1 Adverse Events

All AEs, including non-subject AEs, will be collected throughout a subject's participation, starting from the time the informed consent form is signed, through 30 days after the day of the procedure, regardless of their severity, relationship to the Hugo™ RAS system or study procedures.

After 30 days, all AEs will be assessed by the surgeon and those AEs deemed attributable to the procedure and / or study device will be reported. All deaths will be collected throughout a subject's participation, regardless of relatedness.

Reporting of these events to Medtronic will occur on an AE Form, including event description, date of AE, treatment, resolution, assessment of both the seriousness of the AE and the relatedness to the study device, procedure. Each AE must be recorded on a separate AE eCRF.

AE definitions used in this study (**Table 8**) are based on ISO 14155:2020 (Clinical Investigation of Medical Devices for Human Subjects – Good Clinical Practice). Documented pre-existing conditions are not considered AEs unless the nature or severity of the condition has worsened. See **Section 14** for details regarding AE analyses in each study analysis set. In addition, AEs impacting users or other persons (non-subject AEs) will be collected on a non-subject AE CRF.

Any unresolved procedural or device-related events that are still ongoing past study exit will be monitored by the Investigator per their institutional standard-of-care.

Unavoidable adverse events (UAE) (those that are inherent to the procedure and are expected to occur in all subjects for an expected duration) listed in **Table 11** will not be captured or reported unless the adverse event worsens or persists outside the stated timeframe post procedure. **Section 11.1** includes a list of several but not all-encompassing anticipated adverse events.

All Serious Adverse Events (SAE), deaths, and Surgical Site Events (SSEs) will be adjudicated by an independent CEC through 30 days post-procedure as of revision 5.0 of the protocol.

